9. Vital signs measurement should be performed prior to blood sample collection. At dosing visits a second vital signs measurement should be performed approx. 10 minutes post-dose. Vital signs include DBP/ SBP measurement and pulse rate. Vital signs measurement at Visit 1a is optional but recommended.
10. Body mass index will be calculated automatically. For weight measurement, follow guidelines in [Section 5.1.4](#).
11. For waist and hip circumference measurement, follow guidelines in [Section 5.1.5](#).
12. Safety laboratory tests include haematology, clinical chemistry, coagulation, lipids and urinalysis. For details refer to [Table 5.2.3:1](#). In the event of systemic hypersensitivity ADAs, NAbs, level of BI 456906, IgE, histamine, serum tryptase, and complement components will be analyzed as detailed in the laboratory manual.
13. All blood samples should be collected before the administration of trial medication. Fasting condition is not required for routine trial blood sample collection.
14. RT-PCR test on SARS-CoV-2 will be performed at Visit 1.
15. ECG should be recorded in triplicate at Visit 1. ECG should be recorded before blood samples are taken. ECG recording may be repeated by the Investigator for medical or quality reasons. For ECG measurement, follow guidelines in [Section 5.2.4](#).
16. After the individual patient's end of the trial the Investigator should report only any cancers of new histology and exacerbations of existing cancer, trial treatment related SAEs and trial treatment related AESIs of which the Investigator may become aware of and only via the SAE form.
17. For female patients of childbearing potential only. Xs = serum testing, Xu = urine testing. Serum pregnancy testing will be performed at Visit 1 and thereafter as a reflex test when urine testing is positive. Pregnancy testing must be completed prior to trial medication intake. Refer to [Section 6.1](#).
18. At Visit 16, 20 and 24 the IRT call will only be made if a patient visits the site due to tolerability issues and requires a new assignment of trial medication.

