- Anti-drug antibodies (ADA) and neutralizing antibodies (NAb), peptides as BI 456906 are able to induce antibody development

These side effects, which are known to be dose dependent, can be reduced by careful dose escalation, are easy to monitor, and, therefore, are manageable in clinical trials. In addition, tolerability and safety data is very important in this drug class and plays an essential role in the optimal dose finding. It is also well known that the gastrointestinal disorders are temporary, and most patients adapt to GLP-1R agonist-based compounds during dose escalation and/ or maintenance period.

In this trial the following safety measures will be applied in order to minimize the risk for trial patients:

- An extensive safety laboratory testing will be performed at all site visits.
- Patients with T2DM taking antidiabetic medication will be recommended to measure their fasted blood glucose at home daily and to contact the Investigator for safety related measures.

- If patients develop persistent or recurrent severe hypoglycemic episodes (fasted blood glucose level of 54 mg/dL (3.0 mmol/L) or below) they will be asked to reduce the dose of or discontinue any concomitant antidiabetic medication. Antidiabetic medications are allowed to be interrupted under certain clinical circumstances in order to avoid hypoglycemia. Investigators may decide to keep patients solely on trial treatment if there is evidence of glycemic normalization, which is a well-known effect of glucagon receptor agonists. Hypoglycemic episodes as well as their relationship to the trial treatment will be strictly monitored by investigators and appropriately reported. In patients experiencing hypoglycemia, characteristics of episodes, including frequency and severity, will determine whether hypoglycemia needs to be classified as treatment-related adverse events.
- Patients in the placebo group will remain on standard of care that includes diet and exercise counseling as per local standard, and thorough surveillance.
- There are no risks expected by stopping the trial medication during the course of the trial and no down titration is needed.
- Electrocardiogram (ECG) monitoring will be performed at screening, randomization and at all site visits during the trial, and criteria for heart rate, QT prolongation and cardiac conduction disorders are defined.

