#### 5.2.4 Electrocardiogram

The 12-lead ECG should be collected at the time points specified in the [Flow Chart](#). ECG will be recorded in triplicate at the screening visit, but as a single measurement at the following visits.

Centralized ECG services will be provided by an external vendor for all site visits (including unscheduled visits). Standardized equipment and user manual will be provided by the vendor.

ECG should be collected according to the trial-specific recommendations, using the standardized equipment provided by the vendor. ECGs may be repeated for quality or safety reasons. Patients should be supine for approximately 5-10 minutes before ECG collection. Patients should remain supine, but awake, during the ECG collection process.

ECG recordings will be transmitted electronically to a vendor for central reading. The ECG recordings will be centrally evaluated and rated as normal, abnormal, or unable to evaluate, and the results will be sent to the site. The Investigator should review the report. If the ECG is rated as abnormal, the Investigator will have to determine if the abnormal findings are clinically significant. The Investigator will have the responsibility to follow up with the patient if there are any clinically significant findings in the ECG report.

After the screening visit, the Investigator must review the ECG results from central reading to ensure patient has met all the entry criteria for the trial. Any pre-existing conditions should be recorded as baseline conditions. ECG recorded at the randomization visit should be evaluated by the Investigator before the patient receives the first dose of trial medication. If abnormalities are observed by the Investigator in the ECG reading at randomization visit, the Investigator may wait until the results from central reading are available, and the randomization visit may be rescheduled.

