5.4 OTHER VARIABLE(S)

5.4.1 Safety

Safety will be assessed based on:

- Adverse events
 - Routine reporting using the Medical Dictionary for Regulatory Agencies (MedDRA) coding dictionary (version in force at final DBL)
 - Adverse events of special interest (AESIs)
 - Adjudicated adverse events
- Laboratory variables
 - Specific laboratory tests are listed in CTP Table 5.2.3: 1
- Vital signs
 - Pulse rate
 - Systolic blood pressure
 - Diastolic blood pressure

- 12-lead ECG

Further details regarding 12-lead ECG derivations are given below.

- Columbia - Suicide Severity Rating Scale (C-SSRS)

Laboratory data

Estimated glomerular filtration rate (eGFR) and urine albumin/creatinine ratio (UACR) will be used as provided by the central laboratory, i.e. it will not be re-derived for analysis.

Fib-4 index and APRI will also be used as provided by the central laboratory.

12-lead ECG

Single digital ECG recordings are planned to be collected at each relevant visit with the exception of screening, where triplicate ECG recordings are planned. Each of the recorded single ECGs will then be evaluated for cardiac intervals, which comprise the RR, PR and QT interval and the QRS duration. Measurements of these intervals will be made on four cardiac cycles from the lead chosen (details not specified here).

The measurements of the cardiac cycles will be stored in the database, i.e. four values per visit (for a single ECG). The four cardiac cycles (or however many available) will be averaged, to give a single mean value for each visit. This will be done prior to the calculation below of the heart rate (HR) and heart rate corrected QT interval (QTc).

For screening only, where a triplicate ECG is expected, the mean values obtained for each single ECG will be further averaged across the 3 ECGs (or however many available) to give a single mean value for each variable at screening.

The heart rate will be derived from the RR interval as:

$$\text{HR [beats/min]} = \frac{60\,000}{\overline{RR}}$$

where \overline{RR} is the mean of the four RR intervals (measured in msec).

The QT interval corrected for HR according to Fridericia's formula (QTcF) for a single ECG will be derived as:

$$\overline{QTcF} [\text{msec}] = \left(\frac{1000}{\overline{RR}} \right)^{1/3} * \overline{QT} [\text{msec}],$$

[figure not shown]

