6.7 BASELINE, TIME WINDOWS AND CALCULATED VISITS

Definition of baseline

In general, baseline is defined as the last non-missing measurement on or prior to the first administration of study medication. In the case that the first dose of study medication is delayed beyond the date of randomisation, a post-randomisation value can be used as a baseline value provided that it meets the stated requirement.

Where clock times are available (expected to include laboratory safety data, 12-lead ECG, plasma Survodutide concentrations and biomarkers) they will be used in addition to dates to define baseline, since it is also expected that the time of first study drug administration will be accurately recorded on the eCRF for all patients.

Unscheduled and repeat assessments are eligible for use as baseline values provided that they meet the above criterion.

For 12-lead ECG, if a screening value needs to be used for baseline, it will be the average of all available triplicate screening ECG measurements (see [Section 5.4.1](#) for derivation details).

For vital signs, the baseline definition will make the additional requirement that the data records are pre-dose. In practice, this will also be done using the clock times as well as the date. A single pre-dose measurement is expected to be captured at the baseline visit (Visit 2), which will therefore be used as baseline. In any situation in which only a post-dose measurement is available at Visit 2 and no pre-dose measurements, Visit 2 will not be used as baseline; the screening visit (Visit 1) will be used as baseline instead.

For baseline NAS and fibrosis scores, the following specific considerations will be applied:

- Either a biopsy performed during the screening period or a historical biopsy (within 6 months) will be used to provide baseline data, without any further distinction made for analysis purposes between these two situations (both referred to subsequently as “screening biopsy”).
- The baseline value will be derived from central pathology readings of screening biopsy slides. For sites in all countries except China, central pathology screening readings will always be physical readings. For sites in China, central pathology screening readings may be digital readings, the handling of which is described below.
- All adequate central pathology readings which meet the baseline definition will be used, including any (expected to be occasional) readings performed by the back-up

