Frequency tables will also include morphological findings (determined and categorized based on SDTM terminology) that might be attributable to treatment. In particular, new onsets of findings not present at baseline will be explored. A morphological finding observed on treatment that was not reported at baseline will be categorized as a ‘new onset’ of this finding.

For all patients with any notable finding in ECG intervals, a separate listing will be created as end-of-text display, and the corresponding time profiles will be shown.

A shift table will be produced for QTcF, summarising the shifts from baseline to the maximum value on treatment, and displaying categories “ ≤ 450 msec”, “> 450 to 480 msec”, “> 480 to 500 msec and “> 500 msec”.

A scatter plot of QTcF at baseline and the maximum change from baseline (based on all on-treatment values as defined in [Section 6.1.6](#), and the maximum evaluated regardless of whether these were selected based on visit windows described in [Section 6.7](#)) will be produced. The plot will include diagonal reference lines for absolute QTcF equal to 450 msec, 480 msec and 500 msec, as well as horizontal reference lines for QTcF maximum changes from baseline equal to 30 msec and 60 msec.

Appropriateness of heart rate correction methods of QT interval

To evaluate the appropriateness of the heart rate correction methods, the slope of the relationship of the (untransformed) QTcF interval versus RR interval will be estimated for off-drug values and for each Survodutide maintenance dose group separately by applying a random coefficient (random slope and intercept) model. Off-drug values for this purpose are defined as only values (either baseline or on-treatment values as defined in [Section 6.1.6](#)) from patients randomised to placebo, since patients randomised to Survodutide dose groups are expected to have a single ECG at baseline only, and therefore cannot contribute a slope for estimation of an off-drug random effect for this. For the Survodutide maintenance dose group analyses, only on-treatment values will be used, and these will be included regardless of Survodutide dose (i.e. data from the dose escalation period will be included). The model will be fitted using the QTcF and RR pairs at each time point, using all values within the visit windows defined in [Section 6.7](#). A scatter plot of QTcF versus RR will be produced, and will

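### SAP 7.8.4 takes the off-drug QT/RR slope from placebo patients only, for a reason that fails once the scheduled screening ECG is counted

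*SAP*

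**What the plan says.** SAP 7.8.4 fits random-intercept, random-slope models of QTcF on RR and of log QT on log RR, separately for off-drug values and for each Survodutide maintenance dose group. Off-drug values are the baseline and on-treatment values of patients randomised to placebo. Active patients are left out "since patients randomised to Survodutide dose groups are expected to have a single ECG at baseline only", from which the SAP concludes that they cannot inform an off-drug slope.

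The protocol's ECG schedule is fuller than that:

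- Flow Chart footnote 15: "ECG should be recorded in triplicate at Visit 1".
- Protocol 5.2.4: "ECG will be recorded in triplicate at the screening visit, but as a single measurement at the following visits".
- Protocol 5.2.4 on Visit 2: "ECG recorded at the randomization visit should be evaluated by the Investigator before the patient receives the first dose of trial medication".
- Protocol 1.4.2: "Electrocardiogram (ECG) monitoring will be performed at screening, randomization and at all site visits during the trial".

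The SAP knows of the screening recordings. Section 5.4.1 says: "Single digital ECG recordings are planned to be collected at each relevant visit with the exception of screening, where triplicate ECG recordings are planned", and averages the triplicate to one value per variable. Section 6.7 sets the general rule: "In general, baseline is defined as the last non-missing measurement on or prior to the first administration of study medication". For ECG it adds that "if a screening value needs to be used for baseline, it will be the average of all available triplicate screening ECG measurements", so screening serves as baseline only as a fallback.

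**The concern.** The exclusion of the active arms rests on a single argument: one ECG per patient, hence no slope. That argument depends on which drug-free ECGs are counted. For change from baseline, one baseline value per patient is right. Here the target is the QT/RR relation without drug, and a Visit 1 ECG is as drug-free as a Visit 2 ECG. The SAP gives no reason for passing over the screening value.

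At stake is the precision of the reference slope used to check heart-rate correction. Most of the categorical QT outputs in SAP 7.8.4 rest on QTcF, and the protocol lists conduction disorders and QTc prolongation among known class effects (1.4.2) and reports heart-rate increase with this drug (1.4.3). A check of the correction method should use the drug-free data already collected, or say why it does not.

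**Working it through.** The documents give no precision or sample-size figure for this analysis, so there is nothing of the plan's own to reproduce.

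**Inputs from the documents**

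- 240 patients randomised 1:1:1:1 (Protocol 3.3): 60 placebo, 180 active.
- Pre-dose ECG time points per patient: 2 (Visits 1 and 2), from 3 + 1 = 4 recordings.
- Post-baseline ECG visits marked in the Flow Chart: Visits 4, 6, 8, 10, 12, 14, 18, 22 and 26 to 32, which is 8 + 7 = 15.

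**Counts, assuming complete data**

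- Placebo pairs used now: 60 × (1 + 15) = 960.
- Active pre-dose pairs available: 180 × 2 = 360.
- Active share of the enlarged set: 360 / (960 + 360) = 360/1320 = 27%.
- The placebo screening values are also outside the current definition. Adding them brings 60 more: 420/1380 = 30%.
- Within-patient degrees of freedom: placebo 60 × 15 = 900, active 180 × 1 = 180, so 180/1080 = 17% come from the active arms.

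**Effect on the standard error (within-patient information, QTcF on RR)**

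Each patient contributes information 1 / (τ² + σ²/Sxx) on the population slope. Here τ is the between-patient SD of the slope, σ the residual SD, and Sxx the patient's sum of squares of RR.

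- Placebo, 16 values: Sxx = 15 × SD_RR².
- Active, 2 values: Sxx = d²/2, with d the Visit 1 to Visit 2 difference in RR, taken as normal with variance 2 × SD_RR².

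The variances are assumptions: within-patient SD_RR 50 to 90 ms, σ 8 to 12 ms, τ 0.02 to 0.05. The averaged triplicate is given the same residual variance as a single ECG, which is cautious.

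Mid-grid (SD_RR 70, σ 10, τ 0.035):

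- Placebo Sxx = 15 × 4900 = 73,500, and σ²/Sxx = 100/73,500 = 0.00136.
- Placebo information = 60 / (0.001225 + 0.00136) ≈ 23,200, so SE ≈ 0.0066.
- Active information, averaged over d, ≈ 7,600.
- Combined SE = 1/√30,800 ≈ 0.0057, a fall of about 13%.

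Over the whole grid the fall runs from about 9% (SD_RR 50, σ 12, τ 0.02) to about 23% (SD_RR 90, σ 8, τ 0.05).

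**Second calculation (log QT on log RR, between-patient information included)**

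Assumed SDs on the log scale: RR between patients 0.13 and within patients 0.05 to 0.08, residual 0.025, random intercept 0.04, random slope 0 to 0.15. Adding the active Visit 1 and Visit 2 values lowers the SE by about 16% to 31%. Adding only their Visit 2 value still lowers it by about 8% to 22%. So even one pair per patient informs the population slope through differences in RR between patients, provided that the between-patient and within-patient slopes agree, as the model assumes.

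**The case against.** A reader might infer that the SAP contradicts the protocol by assuming that only one pre-dose ECG exists. The documents do not support that. The SAP's phrase refers to baseline, which section 6.7 defines as the last pre-dose value, and section 5.4.1 describes the screening triplicate. The ECG visit windows in SAP 6.7 start at day 2, so screening also falls outside every window. This is a consistent data selection whose reason is incomplete; it does not deny the schedule.

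A reader might also conclude that three quarters of the pre-dose data are discarded, or that 60 patients are used where 240 could be. Active patients do hold 360/480 = 75% of the pre-dose time points, and 420/480 = 87.5% go unused once placebo screening is counted. Neither figure measures the loss for the slope, which rests mainly on up to 15 on-treatment ECGs per placebo patient.

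The best defence is that the gain is small and optional. Under randomisation, placebo patients are a valid off-drug sample. The slope and its interval are reported in a plot footnote, no hypothesis test is planned for safety, and no threshold is attached. At mid-grid, the 95% half-width for a 100 ms change in RR goes from 1.96 × 0.0066 × 100 ≈ 1.29 ms to 1.96 × 0.0057 × 100 ≈ 1.12 ms of QTcF. If a dose-group slope with the same SE is compared with the reference, the SE of the difference falls only from about 0.0093 to 0.0087, or 6%. All of this stands and limits the weight of the point. It does not repair the stated reason for the exclusion.

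**Conclusion.** The point holds as a minor one. Every active patient is scheduled for two drug-free QT/RR pairs, so the reason given in SAP 7.8.4 for excluding them fails once the screening ECG is admitted. Admitting their pairs adds 360 to at most 960 and lowers the standard error of the off-drug slope by roughly 9% to 23%, about 13% mid-grid. The log-scale calculation, under other assumptions, gives 16% to 31%.

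These percentages rest on complete data and on variances that the documents do not supply. Dropout among placebo patients would raise the active arms' share. The benefit is precision in a supportive, descriptive analysis. There is no reason to expect bias from using placebo alone, and no efficacy result or decision rule is touched.

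**What to change.** In SAP 7.8.4, define off-drug values as:

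- for all treated patients, the Visit 1 value (triplicate averaged to one value as in SAP 5.4.1) and the Visit 2 pre-dose value; and
- for patients randomised to placebo, the on-treatment values as now.

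Keep the same random-coefficient models and delete the rationale that active patients cannot supply a slope. Extend the sentence on visit windows so that pre-dose values are admitted. Where Visit 2 is missing and screening serves as baseline, count that value once.

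Do not enter the three screening recordings separately. The model has no visit-level term, so it would treat same-visit replicates as independent and could make the standard error too small.

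If the sponsor prefers to keep placebo only, one sentence should say why the screening ECG is left out. The cost is a revised SAP sentence and a wider data selection, with no new data.

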7.8.5 Other

Frequency tables will be produced of the information in the C-SSRS questionnaire over time.

7.9 ANALYSIS OF COVID-19 IMPACT

To assess the impact on patients' safety and drug efficacy in this trial, the following analyses are planned:

The frequency of patients with missed relevant visits or early discontinuation from study treatment or study due to COVID-19 and related PDs will be listed and analysed descriptively.

Summary tables and listings of AEs of SARS-CoV-2 infection will be produced. The tables will include an overall summary, a summary by primary SOC and PT, a summary of relevant AEs which led to early treatment discontinuation, and a summary of relevant serious AEs. For this purpose, "SARS-CoV-2 infection" is defined by the broad BICMQ of SARS-CoV-2 infections with search ID 32010051. The broad BICMQ differs from the narrow BICMQ only by the inclusion of the PT for "Suspected COVID-19".

AEs related to SARS-CoV-2 infection will also be summarised and listed. For this purpose, "related to SARS-CoV-2 infection" is defined by the MedDRA broad SMQ for COVID-19.

8. TIMEPOINT OF RELEASE OF TREATMENT INFORMATION

The treatment information will be released to unblind the trial database after the last patient has completed their End-of-Study/Follow-up visit and all data has been entered and cleaned as defined in the “Data Ready to be Unblinded and/or Final Trial Closure Notification” (RUN) form.

11. HISTORY TABLE

Table 11: 1 History table

| Version | Date (DD-MMM-YY) | Author | Sections changed | Brief description of change |
|---------|------------------|--------|----------------------------|--|
| 1.0 | 11DEC2023 | | None | This is the final TSAP |
| 2.0 | 19JAN2024 | | Section 5.1 Section 6.7 | 
This is the revised TSAP.
 
The baseline definition for all biopsy endpoints, including the primary endpoint, has been changed for patients in China, to use the digital reading (1st screening reading) instead of the physical reading (2nd screening reading).
 
This has been done in response to potential analysis model and endpoint derivation issues which were identified from review of these data (transferred to the database 18DEC2023), specifically a thorough consideration of all the implications of physical readings (2nd screening readings) which yielded values outside the eligibility criteria ranges.
 |
